Limited clinical research has been conducted with other amino acid PET tracers in brain metastases, possibly in part due to their highly limited availability in the US. Studies of brain metastases with amino acid PET tracers ¹⁸F-fluoro-ethyltyrosine (¹⁸F-FET), ¹⁸F-fluoro-dihydroxyphenylalanine (¹⁸F-FDOPA) and ¹¹C-methionine have all been described, with demonstration of increased tracer uptake and sensitivities of 79% to 95%, specificities of 84% to 93% for the detection of brain metastases where MRI is suggestive of recurrent disease (Terakawa, 2008; Galldiks, 2012; Lizarraga, 2014; Ciccone, 2015; Minamimoto, 2015; Romagna, 2016; Ceccon, 2017). In recent recommendations by the RANO working group, amino acid PET was recommended as useful in distinguishing post-therapeutic reactive changes following radiotherapy from recurrent brain metastases (Galldiks, 2019). This was based on review of Level 2 evidence on ¹⁸F-FET, ¹⁸F-FDOPA and ¹¹C-methionine. Transport mechanisms of these tracers have overlap with ¹⁸F-fluciclovine, in that these are predominantly LAT1-mediated. Furthermore, known cross-affinity for various amino acids between the 2 transporters support the expectation for ¹⁸F-fluciclovine to demonstrate comparable performance in brain metastases, akin to other amino acid PET tracers and known ¹⁸F-fluciclovine imaging characteristics in glioma. Thus, the investigation of ¹⁸F-fluciclovine in the imaging of brain metastases is of considerable clinical relevance, particularly when considering promising results from the aforementioned IITs of ¹⁸F-fluciclovine in brain metastases.

Amongst the previously cited studies using ¹⁸F-FET, ¹⁸F-FDOPA and ¹¹C-methionine, different interpretation criteria for optimum detection of disease recurrence have been reported. Furthermore, these criteria have been based on different methods of quantifying

PET tracer uptake, and in the case of ¹⁸F-FET, incorporate the interpretation of dynamic scan data (time-activity curves). Therefore, existing heterogeneous data on optimum image interpretation criteria in other amino acid PET tracers cannot be directly applied to ¹⁸F-fluciclovine. Within this clinical program, BED is conducting a Phase 2 study (BED-FLC-219) designed to define image interpretation criteria.

¹⁸F-fluciclovine has a well-established safety profile and a wide distribution network in the US where it is routinely used as standard of care (SoC) for imaging in biochemical recurrence of prostate cancer.

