The on-site investigator will also review the ¹⁸F-fluciclovine PET scan to identify potential additional lesions, not previously reported on SoC MRI (termed 'additional PET lesions'). Additional PET lesions should be annotated only where judged suggestive of brain metastasis, warranting confirmation by clinical follow-up, biopsy or resection, according to SoC practice. Undertaking biopsy/resection of additional PET lesion(s) identified on the ¹⁸F-fluciclovine PET scan is at the discretion of on-site investigators. Moreover, an additional PET lesion should be discrete and spatially separate from known, pre-existing lesions. In particular, the following should **not** be annotated as Additional PET lesions: known pre-existing non-progressive lesions (considered at site level as stable or partially responding), ¹⁸F-fluciclovine activity contiguous with a known lesion (previously annotated or otherwise) and apparently incongruent with the lesion's outline on correlating MRI, particularly where this may be reasonably explained by image registration.

For subjects due for pre-planned SoC biopsy/neurosurgical intervention, the procedure will be at Visit 4. The subject will receive post-procedural management per institutional SoC. All ongoing follow-up and any further treatment will be in accordance with SoC. Samples obtained during this Visit 4 will be subject to central histopathological evaluation.

As with subjects who undergo pre-planned SoC biopsy/neurosurgical intervention, subjects pre-planned for clinical follow-up to evaluate the equivocal lesions will undergo follow-up performed as SoC per local practice. This is anticipated to vary between subjects.

The final visit for each subject, including subjects who had undergone pre-planned SoC biopsy/neurosurgical intervention, will usually be the Month-6 Follow-up at Visit 5. For study purposes, clinical data accrued during SoC clinical follow-up, pertaining to the ongoing assessment, eventual confirmation of diagnosis, and treatment of the lesions, will be collected. The data will comprise brain imaging scans, treatment regimens, histopathological reports and mortality status. The period of data accrual will be up to 6 months following ¹⁸F-fluciclovine PET, or death, whichever comes first. Subjects still considered equivocal at site level at Month 6 (Visit 5) will undergo a study MRI.

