11.8.3. Blinded Image Evaluation

A 3-reader central, independent BIE of the ¹⁸F-fluciclovine PET scans will be performed, diagnosing recurrent metastasis (positive) vs no recurrent metastasis (negative) for each reference lesion, other equivocal lesion(s) and additional PET lesion(s), using the Visit 2 MRI for anatomical reference.

- Image criteria used in the BIE will be informed by a Phase 2b study (BED-FLC-219).
- Inter- and intra-reader concordance will be measured.
- The readers will not have access to clinical history, prior clinical imaging, any site-generated diagnostic evidence, nor the final patient outcome.

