15.6.2. Lesion-Level Diagnostic Performance

Lesion-level diagnostic performance (lesion level PPA, NPA, PPV and NPV) will be calculated based on BIE of ¹⁸F-fluciclovine PET compared to SoR on all lesions (reference, other equivocal and additional PET lesions).

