7.4.4.2 Lesion-Level Diagnostic Performance

Lesion-level diagnostic performance (lesion-level PPA, NPA, PPV and NPV) will be calculated based on BIE of ^{18}F -fluciclovine PET compared to SoR on all lesions (reference, other equivocal and additional PET lesions) as determined by CTP (i.e. if CTP decides that the lesion SoR is indeterminate, then the lesion will not be counted in this lesion-level diagnostic performance). Point estimates and 95% 2-sided confidence intervals will be presented.

The confidence interval will be calculated based on the methodology described by Zhou et al, for lesion-level PPA, NPA, PPV and NPV. The formula for PPV is:

$$\widehat{PPV} = \sum_p TP_p / \sum_p Pos_p$$
$$\widehat{Var}(\widehat{PPV}) = \frac{1}{P(P-1)} \sum_p \left(\frac{Pos_p}{\overline{Pos}} \right)^2 (\widehat{PPV}_p - \widehat{PPV})^2$$

With:

P	: (number of) Patients
p	: individual patient
Pos_p	: Number of positive regions for patient p
TP_p	: Number of true positive regions for patient p
$\overline{Pos} = \sum_p Pos_p / P$: Mean cluster size
$\widehat{PPV}_p = TP_p / Pos_p$: Patient PPV

The example in Zhou et al. is coded in SAS in Appendix 1.

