Subjects with additional metastases identified on ^{18}F -fluciclovine PET but not on SoC MRI are those with at least one lesion with type = 'Additional PET Lesion' on the lesion annotation eCRF page, which has SoR = 'positive' according to the CTP. Lesions that are deemed to have SoR = 'indeterminate' by CTP will not be considered as additional metastases.

The estimate of the proportion of subjects and the associated 95% 2-sided exact confidence interval (Clopper-Pearson) will be presented.

7.4.4.4.3 Proportion of subjects whose prospective diagnostic management plan changes following ^{18}F -fluciclovine PET.

The proportion of subjects whose prospective diagnostic management plan changes following ^{18}F -fluciclovine PET will be established by comparing the diagnostic management plan of the reference lesion before and after ^{18}F -fluciclovine PET.

The intended diagnostic management plan on the reference lesion will be recorded at visit 1 as craniotomy, biopsy, biopsy in context of LITT, or clinical follow-up. At visit 2, post ^{18}F -fluciclovine PET, the diagnostic plan will be recorded again. If a different option has been chosen, or if there are any additional/new subject management activities planned then this will be counted as a change.

The estimate of the proportion of subjects and the associated 95% 2-sided exact confidence interval (Clopper-Pearson) will be presented.

7.4.4.5 *Inter-Reader / Intra-Reader Agreement (Blinded Image Evaluation)*

For inter-reader agreement, pairwise comparisons of the ¹⁸F-fluciclovine PET scan central reads for the 3 readers (i.e. Reader 1 vs Reader 2, Reader 1 vs Reader 3, and Reader 2 vs Reader 3) will be performed at the subject-level (i.e., reference lesion only) and also at the lesion-level (i.e., all lesions defined by site). The number and percentage of each combination of results (Positive [1st reader] / Positive [2nd reader], Positive/Negative, Negative/Positive, Negative/Negative) will be presented, along with the number and percentage of results in agreement and disagreement. Cohen's kappa statistic will be calculated and presented for each pairwise comparison of the 3 readers, with the corresponding 95% CI and p-value.

Similar statistics will be presented for intra-reader agreement (10% of subjects) – comparisons will be between the initial read vs re-read of a subset of PET scans for each reader.

7.4.4.6 *Sensitivity Analyses*

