7.4.5 Statistical/Analytical Issues

7.4.5.1 Handling of Dropouts or Missing Data

Data imputation on missing or indeterminate SoR from the Central Truth Panel on the reference lesion (i.e. subject level only) will be performed according to the following chart:

If the SoR determined by the CTP is not positive/negative then the SoR will be determined using the following rules:

1. If the subject has neurological deterioration at any time during the 6-months follow-up, the SoR will be assigned to positive.
2. If the subject is confirmed not to have neurological deterioration on or after day 141 (6 months with a 4-week time window, i.e. day 169 with a 28-day time window), even if the subject dies after day 141, the SoR will be assigned to negative.
3. Otherwise the SoR will remain as indeterminate.

All subject-level analysis involving SoR will be presented twice, by imputing the remaining indeterminate results as follows:

1. Main analysis of primary and secondary endpoints on subject level diagnostic performance – for each PET reader, the worst case according to that reader (i.e. the opposite finding to the individual PET reader finding) will be imputed
2. Sensitivity analysis 1 of primary and secondary endpoints on subject level diagnostic performance - for each PET reader, the worst case according to the majority of PET readers (i.e. the opposite finding to the PET finding of at least 2/3 PET readers)

To check the validity of the results based on the site's determination of the reference equivocal lesions, these lesions will be measured and confirmed by the central neuroradiologist. A sensitivity analysis on the main endpoint of subject level PPA and NPA, using only subjects with central neuroradiologist confirmation of the reference equivocal lesions, will be performed if there is discrepancy between the site confirmation of reference equivocal lesions vs the central neuroradiologist confirmation.

For lesion level analysis, none of the lesions will be imputed if the SoR designation from the CTP is missing or indeterminate. Lesion-level analysis will only include lesions with SoR designation of positive or negative by the CTP.

7.4.5.2 *Interim Analyses and Data Monitoring*

Not applicable.

7.4.5.3 *Multicenter Studies*

This is a multicenter study, with approximately 18 sites expected to participate. Data collected from all study sites will be pooled for data analysis.

7.4.5.4 *Multiple Comparisons/Multiplicity*

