7.6 Determination of Sample Size

Approximately 150 subjects will be enrolled, to obtain 130 evaluable subjects.

A one-sample binomial exact test will be used to test the following hypotheses in NPA and PPA of ^{18}F -fluciclovine PET:

NPA

- $H_0(\text{NPA})$: NPA of PET $\leq \text{NPA}_0$
- $H_1(\text{NPA})$: NPA of PET $> \text{NPA}_0$

PPA

- $H_0(\text{PPA})$: PPA of PET $\leq \text{PPA}_0$
- $H_1(\text{PPA})$: PPA of PET $> \text{PPA}_0$

Where NPA_0 and PPA_0 are performance goals for NPA and PPA, respectively.

Performance goals of 50% (NPA_0) for NPA and 50% (PPA_0) for PPA were selected as acceptable thresholds given the setting where SoC imaging is already equivocal. The lower limits for the exact 95% confidence intervals (Clopper-Pearson method) for both NPA and PPA should be greater than 50%. Assuming a NPA of at least 70% and PPA of at least 70% for ^{18}F -fluciclovine PET would need to be observed, a sample size of 130 would achieve 90% power at a 1-sided significance level of 0.025 to reject the performance goals for both NPA and PPA; assuming a brain metastasis prevalence rate of 0.5.

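### Lesion-level PPA and NPA pool MRI-selected lesions with lesions selected on the study PET itself, and no lesion-level performance analysis separates the two (minor)

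*SAP*

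**What the plan says.** Protocol 15.6.2 calculates all four lesion-level measures from the blinded reads "compared to SoR on all lesions (reference, other equivocal and additional PET lesions"), and SAP 7.4.4.2 repeats this with the Central Truth Panel (CTP) as arbiter: "compared to SoR on all lesions (reference, other equivocal and additional PET lesions) as determined by CTP".

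The three lesion types enter by different routes. Protocol 4.1 and 9.1.5 and SAP 6.1 fix the reference and other equivocal lesions on the pre-study standard-of-care MRI. The same sections create the third type from the site's review of the study PET, for findings that the earlier MRI did not report: "Additional PET lesions should be annotated only where judged suggestive of brain metastasis".

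Under protocol 11.8.3 three central readers score every listed lesion on that same PET. They are blinded: "The readers will not have access to clinical history, prior clinical imaging, any site-generated diagnostic evidence, nor the final patient outcome". SAP 7.4.4.5 describes the lesion-level set as the lesions defined by the site. Indeterminate lesions drop out under SAP 7.4.5.1: "Lesion-level analysis will only include lesions with SoR designation of positive or negative by the CTP".

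**The concern.** PPA and NPA are presented as sensitivity and specificity. Those readings need lesions that were sampled without regard to the test result. Here one lesion type is sampled through the test. A metastasis that was not reported on the standard-of-care MRI and was missed on the site's PET review has no way into the pool as a false negative. A non-metastatic site that was off that MRI and PET-negative has no way in as a true negative. A PET-only finding that the CTP judges negative can enter, and by then the site has already found it suggestive on the same scan.

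The rest of the plan does not expose this. The subgroups in SAP 7.4.4.3 and the sensitivity analyses in 7.4.4.6 and 7.4.5.1 are at subject level. SAP 7.4.4.4.2 counts only subjects with at least one CTP-positive additional lesion. The cluster-adjusted variance in 7.4.4.2 deals with correlation within a patient, not with selection. At stake is whether the lesion-level figures describe reader accuracy or partly describe how many extra lesions the sites annotated.

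**Working it through.** **The plan's own figures.** The documents give no lesion count, goal or power for the lesion-level analysis. The only design figure is the 90% power of the subject-level tests in SAP 7.6. With 65 subjects per truth class, a 50% goal, a 70% true rate and one-sided 0.025, the exact test rejects at 41 or more of 65 and has power 0.910 per test. That figure reproduces per test, and it does not involve lesion-level data.

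**Inputs.**
- Base PPA and NPA of 70%, and half of lesions positive: borrowed from the subject-level assumptions in SAP 7.6.
- An alternative base of 90%: chosen because protocol section 2 reports, for other amino acid tracers, "sensitivities of 79% to 95%, specificities of 84% to 93% for the detection of brain metastases".
- 170 MRI-defined lesions (85 CTP-positive, 85 CTP-negative), N additional lesions, 60% of them CTP-positive, and the reader call rates: all assumed.

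**Formulas.** Let S and C be the base PPA and NPA. Let a⁺ and a⁻ be the CTP-positive and CTP-negative additional lesions, and r⁺ and r⁻ the shares of each that a blinded reader calls positive.
- Pooled PPA = (85·S + a⁺·r⁺) / (85 + a⁺)
- Pooled NPA = (85·C + a⁻·(1 − r⁻)) / (85 + a⁻)
- Shift in PPA = a⁺(r⁺ − S) / (85 + a⁺). It is zero at r⁺ = S.
- Shift in NPA = a⁻(1 − r⁻ − C) / (85 + a⁻). It is zero at r⁻ = 1 − C, and negative above that.

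**Break-even.** Base 70%, N = 20 (12 positive, 8 negative), r⁺ = 70%, r⁻ = 30%: PPA = (59.5 + 8.4)/97 = 70.0% and NPA = (59.5 + 5.6)/93 = 70.0%. Nothing moves.

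**Changing only the number annotated.**

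| Base | r⁺ / r⁻ | N | Pooled PPA | Pooled NPA |
|---|---|---|---|---|
| 70% | 90% / 60% | 5 | 62.2/88 = 70.7% | 60.3/87 = 69.3% |
| 70% | 90% / 60% | 20 | 70.3/97 = 72.5% | 62.7/93 = 67.4% |
| 70% | 90% / 60% | 40 | 81.1/109 = 74.4% | 65.9/101 = 65.2% |
| 90% | 80% / 60% | 5 | 78.9/88 = 89.7% | 77.3/87 = 88.9% |
| 90% | 80% / 60% | 20 | 86.1/97 = 88.8% | 79.7/93 = 85.7% |
| 90% | 80% / 60% | 40 | 95.7/109 = 87.8% | 82.9/101 = 82.1% |

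PPA can also fall at the lower base: with r⁺ = 60% and N = 20 it is (59.5 + 7.2)/97 = 68.8%.

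**Range.** Let N run from 5 to 40, with 40% or 60% CTP-positive, none or half of the remainder indeterminate, r⁺ from 60% to 90% and r⁻ from 30% to 90%. At base 70%, PPA runs from 67.8% to 74.4% and NPA from 56.8% to 70.0%. At base 90%, PPA runs from 83.4% to 90.0% and NPA from 72.4% to 89.8%. Because r⁺ is capped at 90%, PPA cannot rise in the base-90% range; that is a product of the grid, not a result.

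**After restriction to MRI-defined lesions.** Both measures stay at their base value for any N.

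**The case against.** The strongest reply is that pooling is the protocol's own definition, that any pooled proportion depends on its mix, and that the present plan is conservative where a direction can be expected, since pooling charges PET-only false positives against NPA. Replacing the pool with MRI-defined lesions would remove those errors. It would also remove blinded-reader misses of CTP-positive additional lesions: in the base-90%, N = 20 case, dropping them lifts PPA from 88.8% to 90.0%. This stands, and it is why the pooled analysis should be kept.

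The size is also modest and assumed. At base 70% and N = 20 the shifts are about 2.5 points. A simple 95% half-width on 85 lesions is 1.96·√(0.7·0.3/85), or about 9.7 points, ignoring clustering. The NPA of 56.8% needs 40 determinate additional lesions, 60% of them CTP-negative and 90% of those called positive. Annotation is further limited to discrete lesions separate from known ones. SAP 7.1.1 also promises listings of the eCRF and image data, although a listing is not a planned analysis.

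Stronger readings are tempting. A reader might infer that additional PET lesions are positive by definition in the blinded evaluation. They are not: entry depends on the site's read, and the blinded readers can call them negative. A reader might infer that pooling inflates PPA, or that both measures always move with the number annotated. The break-even case and the falling-PPA cases show otherwise. Finally, removing the pooling would not make the lesion-level and subject-level results fully comparable, because SAP 7.4.5.1 imputes indeterminate truth at subject level and excludes it at lesion level.

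**Conclusion.** The point holds in a limited form. The pooled lesion-level PPA and NPA are partly selected on the index test, and they move with the number of additional PET lesions whenever reader call rates in those lesions differ from the rates in MRI-defined lesions. Only the fall in NPA has an expected direction, because the site has already judged the same scan suggestive; it requires r⁻ above 30% at a base NPA of 70%, or above 10% at 90%. PPA has no established direction. Lesion-level PPV is less open to the objection, since it conditions on a positive read.

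The selection is certain from the text; its size is not, and every count and call rate above is an assumption. The endpoint is secondary with no performance goal. The primary endpoint and its success rule use the reference lesion alone and are unaffected, so the documents do not support reading this as a threat to the trial's main conclusion. Severity is minor.

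**What to change.** Keep the pooled analysis in SAP 7.4.4.2 and add:

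> For each reader, lesion-level PPA, NPA, PPV and NPV will also be calculated on MRI-defined lesions only (reference and other equivocal) with a positive or negative SoR. This result will be used when lesion-level PPA and NPA are interpreted as sensitivity and specificity. Additional PET lesions will be tabulated separately: number annotated; number with missing or indeterminate SoR; proportion CTP-positive among those with a determinate SoR; and, for each reader, the full 2x2 counts against SoR (including CTP-positive lesions read negative and CTP-negative lesions read positive) and the PPV. The cluster-adjusted interval will be used, or counts only where its variance is zero or undefined.

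Record the addition in SAP 7.7, which at present reports no changes; protocol section 15 requires the SAP to document changes to the planned analyses.

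The cost is one extra set of tables. Lesion type is already held "on the lesion annotation eCRF page" (SAP 7.4.4.4.2), so no new data and no change to the reads are needed. The MRI-only figures leave out errors in PET-only lesions, but these stay visible in the pooled and separate tables.

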7.4.4.3 Subgroup Analysis of Diagnostic Performance Data

Subgroup analyses of subject-level PPA, NPA, PPV, and NPV of ¹⁸F-fluciclovine PET, will also be presented. Subgroups will be as follows, and the calculations will only be performed when there are at least 10 observations in the subgroup:

Age Group:

- <65 years old
- ≥ 65 years old

Sex:

- Male
- Female

Race:

- American Indian or Alaska Native
- Asian
- Black or African American
- Native Hawaiian or Other Pacific Islander
- White

Primary Tumor Type:

- Melanoma
- Breast
- Lung Cancer (NSCLC and SCLC)
- Gastrointestinal (Colorectal and Pancreatic)
- Genitourinary (Bladder, Kidney, Testes)
- Non-Lung/Breast/Melanoma

Concurrent Immunotherapy:

- Received Concurrent Immunotherapy
- Did Not Receive Concurrent Immunotherapy

7.4.4.4 *Clinical Usefulness*

7.4.4.4.1 Number of Days taken by the site to establish presence/absence of metastasis by clinical follow-up

The number of days taken by the site to establish presence/absence of metastasis for each lesion, by clinical follow up, will be defined as the time from administration of ^{18}F -fluciclovine to the date the presence or absence of metastasis is determined in each lesion by the site. Analysis will be performed at the lesion-level (including all lesions - reference, other equivocal, additional PET) recorded on the lesion annotation page of the eCRF, and at the subject-level (based on the reference lesion only).

If the presence or absence of metastasis is not ascertained by the time the subject reaches the end of the follow-up or when the subject prematurely withdraws from the study, the lesion/subject will be censored on the date the subject withdraws from the study. The number of diagnoses ascertained and the number censored will be summarized. Kaplan-Meier methodology will be used to handle the censoring of the data, and to estimate the median time to establish presence/absence of metastasis. The range of days taken to establish presence/absence will be presented for all lesions/subjects and also for uncensored lesions/subjects.

7.4.4.4.2 Proportion of subjects with additional metastases identified on ^{18}F -fluciclovine PET in addition to standard of care brain MRI.

Subjects with additional metastases identified on ^{18}F -fluciclovine PET but not on SoC MRI are those with at least one lesion with type = 'Additional PET Lesion' on the lesion annotation eCRF page, which has SoR = 'positive' according to the CTP. Lesions that are deemed to have SoR = 'indeterminate' by CTP will not be considered as additional metastases.

The estimate of the proportion of subjects and the associated 95% 2-sided exact confidence interval (Clopper-Pearson) will be presented.

7.4.4.4.3 Proportion of subjects whose prospective diagnostic management plan changes following ^{18}F -fluciclovine PET.

The proportion of subjects whose prospective diagnostic management plan changes following ^{18}F -fluciclovine PET will be established by comparing the diagnostic management plan of the reference lesion before and after ^{18}F -fluciclovine PET.

The intended diagnostic management plan on the reference lesion will be recorded at visit 1 as craniotomy, biopsy, biopsy in context of LITT, or clinical follow-up. At visit 2, post ^{18}F -fluciclovine PET, the diagnostic plan will be recorded again. If a different option has been chosen, or if there are any additional/new subject management activities planned then this will be counted as a change.

The estimate of the proportion of subjects and the associated 95% 2-sided exact confidence interval (Clopper-Pearson) will be presented.

7.4.4.5 *Inter-Reader / Intra-Reader Agreement (Blinded Image Evaluation)*

For inter-reader agreement, pairwise comparisons of the ¹⁸F-fluciclovine PET scan central reads for the 3 readers (i.e. Reader 1 vs Reader 2, Reader 1 vs Reader 3, and Reader 2 vs Reader 3) will be performed at the subject-level (i.e., reference lesion only) and also at the lesion-level (i.e., all lesions defined by site). The number and percentage of each combination of results (Positive [1st reader] / Positive [2nd reader], Positive/Negative, Negative/Positive, Negative/Negative) will be presented, along with the number and percentage of results in agreement and disagreement. Cohen's kappa statistic will be calculated and presented for each pairwise comparison of the 3 readers, with the corresponding 95% CI and p-value.

Similar statistics will be presented for intra-reader agreement (10% of subjects) – comparisons will be between the initial read vs re-read of a subset of PET scans for each reader.

7.4.4.6 *Sensitivity Analyses*

7.4.4.6.1 Analysis 1: Subject-Level NPA and PPA on subjects with histopathology or follow-up MRI prior to CNS-directed therapy

Subject-level NPA and PPA (equivalent to specificity and sensitivity, respectively) of ¹⁸F-fluciclovine PET in detecting recurrent brain metastases will be calculated for subjects who either have histopathology available, or have follow-up MRI acquired before new or altered CNS-directed therapy and have lesions with at least 20% increase or 30% decrease in the longest diameter relative to the SoC baseline MRI.

The SoR will be based on CTP determination on the two corresponding domains: histopathology and on MRI findings before new or altered CNS-directed therapy.

- SoR will be positive if one domain is positive and the other domain is positive or non-contributory.
- SoR will be negative if one domain is negative and the other domain is negative or non-contributory.
- SoR will be indeterminate if both domains are non-contributory, or if one domain is positive and the other domain is negative.

7.4.4.6.2 Analysis 2: Subject-Level NPA and PPA on subjects without contributory MRI findings after new or altered CNS-directed therapy

Subject-level NPA and PPA (equivalent to specificity and sensitivity, respectively) of ¹⁸F-fluciclovine PET in detecting recurrent brain metastases will be calculated for subjects who:

[figure not shown]
- have no CNS-directed therapy during follow-up, or
- have non-contributory findings in MRIs acquired after new or altered CNS-directed therapy.

The SoR will be based on the final CTP determination in these subjects.

